**1. PROJECT TITLE**

Effect of Ivabradine on Patients with Postural orthostatic tachycardia syndrome (a double-blind placebo-parallel group trial)

**4. ESTIMATED DURATION OF THE STUDY**

1 year

**5. LAY LANGUAGE SUMMARY OR SYNOPSIS (no more than one paragraph)**

Postural orthostatic tachycardia syndrome (POTS) occurs in approximately 500,000 Americans, but predominates in women with a 5:1 ratio. Patients with POTS experience debilitating tachycardia upon postural changes such as standing that impairs their quality of life. Tachycardia is clinically defined as a heart rate greater than 100 beats/min; and in POTS patients, the prolonged heart rate increase is greater than 30 beats/min or increases to 120 beats/min within the first ten minutes of a diagnostic tilt table test without postural hypotension. There are currently no effective treatment methods for POTS. However, several studies suggest Ivabradine could be a main treatment option for POTS because Ivabradine specifically inhibits the f-channels (If) within the sinoatrial (SA) node, which slows the heart rate. Currently in the US, Ivabradine is mainly prescribed to treat chronic heart failure. It is well tolerated in patients, but it is not commonly prescribed for POTS. It has been also used for treatment of inappropriate sinus tachycardia with good benefit. We hypothesize that Ivabradine will reduce tachycardia and improve functional status in patients with POTS.

**6. SPECIFIC AIMS**

The major objective of this proof-of-concept study is to gain clinical evidence to utilize Ivabradine as a treatment option for POTS. Preliminary data indicates that such an expectation is possible given the fact that Ivabradine has been proven to decrease heart rate.

We will conduct a randomized double-blind placebo controlled clinical trial with a double cross over design. 20 patients with POTS will receive Ivabradine treatment vs placebo for one month. Then there will be a one-week wash out period prior to the cross over in which patients who received Ivabradine will receive the placebo, and patients who initially were on placebo will now receive Ivabradine. We will compare heart rates in both groups after one-month of intervention. We will assess if Ivabradine mitigates patient symptoms and increases patient adherence. This work will help translate our research on beneficial effects of Ivabradine into a clinically relevant patient population.

We will test this hypothesis by pursuing the following aim:

### **Specific Aim 1: Evaluate the change in heart rate**

*Hypothesis: Ivabradine will reduce tachycardia and improve functional status in patients with POTS.*

We propose to test this hypothesis in a randomized double-blind placebo-controlled with a cross over clinical trial in which otherwise healthy patients diagnosed with POTS will be randomized into Ivabradine or placebo group treatment for one month then crossed over to the other group for another month (one week wash-out period before cross over). Patients will undergo a baseline tilt table test, norepinephrine bloodwork, and quality of life (QOL) questionnaires.

- Primary endpoint:
  - Change in heart rate after one month of Ivabradine intervention compared to baseline.
- Secondary endpoint:
  - Quality of life measured with questionnaires after one month of Ivabradine intervention compared to baseline.

We will assess:

- *Effects on tachycardia (table tilt test)*
- *Orthostatic heart rate monitoring*
- *Symptomatic changes (QOL questionnaire)*

*Results will provide significant understanding of mechanisms that underlie sympathetic hyperactivation and provide a potential avenue for an effective and safe treatment with Ivabradine with the ultimate goal of increasing patient adherence and reducing debilitating patient symptoms.*

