## **9. RESEARCH DESIGN AND METHODS**

**Overall Study Design.** The clinical trial will be registered under [www.clinicaltrials.gov](http://www.clinicaltrials.gov). Subjects between the ages of 18-65 who have a POTS diagnosis will be enrolled. Specifically, we will enroll patients who have hyperadrenergic POTS as confirmed by norepinephrine (NE) levels > 600 pg/ml. This is a 3-month study with a randomized double-blind placebo controlled cross over design. Subjects will be randomized into one of two groups (Ivabradine or placebo for one-month) then crossed over after a one-week washout period to the other group for one-month. Refer to Figure 1 below for details.

[figure not shown]

Figure 1. Randomized double-blind placebo-parallel group crossover trial with Ivabradine for patients with POTS.

**Study Visits.** There will be seven visits at the ACTRI and UCSD Cardiology clinics.

-Visit 1 is the pre-screening visit during which norepinephrine (NE) blood results will be obtained to confirm hyperadrenergic POTS diagnosis (NE> 600pg/ml). Orthostatic heart rate will be monitored. A urine pregnancy test will also be administered at this time. Post-menopausal women and women who are infertile will not be asked to take pregnancy test per PI discretion.

-At Visit 2, baseline lab work will be obtained to assess cardiometabolic health (CBC, CMP, TSH, T4, BNP). A tilt table test will be performed to determine baseline heart rate and QOL questionnaire (ShortForm36, SF36) will be completed. Orthostatic heart rate will be monitored. At this point, the patient will be randomized into the Ivabradine or placebo group for one month.

-At Visit 3, two-weeks into treatment, the patient will return to ACTRI for drug titration. Orthostatic heart rate will be monitored. If the patient fulfills criteria (see **Ivabradine Dosing** below), they will either increase, decrease, stop, or not change their Ivabradine dose.

-At Visit 4, one month after starting the current treatment, orthostatic heart rate monitoring, NE bloodwork, and QOL questionnaires will be completed. There will be a one-week wash-out period before the patient crosses over to the other group for one month.

-At Visit 5, the patient will return for orthostatic heart rate monitoring, NE bloodwork, and QOL questionnaires. A urine pregnancy test will be administered at this time. Post-menopausal women and women

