who are infertile will not be asked to take pregnancy test per PI discretion. The patient will be instructed to begin the secondary treatment (placebo or Ivabradine) for one month.

-At Visit 6, two-weeks into this treatment, the patient will return to ACTRI for drug titration. Orthostatic heart rate will be monitored. If the patient fulfills criteria (see **Ivabradine Dosing** below), they will either increase, decrease, stop, or not change their Ivabradine dose.

-At Visit 7, one month after starting the secondary treatment, the patient will return for orthostatic heart rate monitoring, NE bloodwork, and QOL questionnaires.

Blood samples will be saved and securely stored with the PI for future research analysis and purposes.

**Randomization.** Randomization refers to the order in which patients receive placebo or Ivabradine. If a patient receives Ivabradine first for one month, then he/she will be switched over to placebo for one month. If a patient receives placebo first for one month, then he/she will be switched over to Ivabradine for one month. There will be a one-week washout period prior to the cross-over. There will be 10 patients in each group.

**Ivabradine Dosing.** Ivabradine dose will initiate at 5mg twice daily (bid) and be increased to 7.5mg twice daily (bid) after 2 weeks if the heart rate is greater than 70 beats/min. If the heart rate is less than 70 beats/min there will no increase in dose. If the heart rate is less than 50 beats/min, or if the patient has symptoms of dizziness or lightheadedness, then Ivabradine will be stopped.

If patients have side effects and feel that cannot continue with Ivabradine we will decrease the dose from 7.5mg bid to 5mg bid (or if they are on 5mg bid to 2.5mg bid). After this dose reduction if the patient is still unable to tolerate Ivabradine, we will stop Ivabradine and withdraw patient from the study. If a patient is unable to tolerate Ivabradine (particularly prior to crossover period), he/she will be withdrawn. The starting dose and titration model is the same for the crossover treatment period as the initial month.

In our clinical experience using Ivabradine in patients with inappropriate sinus tachycardia (which are very similar to POTS patients in age and co-morbidities) we have not seen significant side effects that have caused patients to stop the drug. Refer to the uploaded Ivabradine Drug Information document for more details.

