**Specific Protocols.** Brief synopsis of methods currently used is provided below.

**Tilt Table Test:** Only the physician PIs will perform the tilt table test with assistance from the medical staff of the UCSD Medical Center.

**Orthostatic Heart Rate Monitoring:** First, the patient's heart rate will be measured at rest after lying down for 3 minutes. Then, the patient will be asked to stand and the standing heart rate will be measured after 3 minutes. The changes in position with 3 minute intervals will establish the orthostatic heart rate.

**Quality of Life (QOL) Questionnaire:** Patients will complete the Short Form-36 (SF36) subjective questionnaire to aid in analysis of patient symptoms before/after each treatment period.

**Blood Tests:** The following blood tests will be processed at UCSD Clinical Laboratories: 1) Cardiometabolic parameters: (CBC, CMP, TSH, T4, BNP) and 2) norepinephrine levels (NE).

The 2-3-month time period will be used as prior literature suggests that this length of therapy is needed to trigger pharmaceutical changes to translate into functional endpoints.

**Assessments.** We will assess for patient improvement with tilt table testing, orthostatic heart rate monitoring, labs, and quality of life (QOL) questionnaires before and after treatment. The patient will undergo a baseline norepinephrine workup and a baseline tilt table test; if the patient is on Midodrine, Florinef, or Ivabradine, there will be a one week washout period. The patient will then be randomized into the Ivabradine or the placebo group for one month. After this one month, they will undergo orthostatic heart rate monitoring, blood work for norepinephrine levels, and QOL questionnaires. There will be a one week washout period before they are crossed over to the other therapy (placebo vs Ivabradine) for one month. The washout period protocol

---

includes maintaining a stable salt and fluid intake. Once crossed over, they will repeat an orthostatic heart rate monitoring, blood work for norepinephrine levels, and QOL questionnaires.

We will continuously assess for all adverse events throughout the study. Some of these labeled adverse reactions may include bradycardia, hypertension, atrial fibrillation, and visual distortions (visual brightness, diplopia, visual impairment, phosphenes).

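### The primary heart-rate endpoint names no posture or summary measure, its baseline is assigned to a tilt test that the visit text does not repeat after treatment, and the period-2 baseline is not stated

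*Combined protocol and SAP*

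**What the plan says.** **Endpoint.** Specific Aim 1 gives the primary endpoint as "Change in heart rate after one month of Ivabradine intervention compared to baseline". Section 6 says "We will compare heart rates in both groups after one-month of intervention". Neither names a posture or a test.

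**Baseline.** In Section 9, Study Visits, for Visit 2: "A tilt table test will be performed to determine baseline heart rate". An orthostatic heart rate is also taken at that visit.

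**After treatment and after washout.** The same section has:
- "At Visit 4, one month after starting the current treatment, orthostatic heart rate monitoring, NE bloodwork, and QOL questionnaires will be completed";
- "At Visit 5, the patient will return for orthostatic heart rate monitoring, NE bloodwork, and QOL questionnaires";
- "At Visit 7, one month after starting the secondary treatment, the patient will return for orthostatic heart rate monitoring, NE bloodwork, and QOL questionnaires".

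None of these three visits includes a tilt test.

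**The orthostatic procedure.** Heart rate is read after 3 minutes lying, then "the standing heart rate will be measured after 3 minutes". The description ends: "The changes in position with 3 minute intervals will establish the orthostatic heart rate". That may point to the lying-to-standing rise, but nothing links it to the endpoint.

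**Analysis and power.** Section 9, Statistical Analysis, summarises a mean and a maximum heart rate and compares one-month changes from baseline by t-tests. Power Analysis uses a 10 beats/min fall in an average heart rate, with 100 to 90 as the example, and an SD of 7.5. Sections 10 and 11 repeat the average. None of these terms is tied to a posture or test.

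**Tilt as an outcome.** Specific Aim 1 lists tilt testing among the effects to be assessed, and Section 9, Assessments, lists it before and after treatment. The later sentences of Assessments that describe the post-treatment work-up omit it. Drop-outs adds an attempted tilt test when a patient withdraws for intolerance.

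**The concern.** Lying rate, standing rate and rise are different endpoints. Section 5 describes the disease by a rise of more than 30 beats/min or by reaching 120 beats/min. A drug that lowers both postures by the same amount changes the level and leaves the rise unchanged. The unnamed posture therefore affects what a positive result would mean.

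The baseline rule is a separate defect. Section 14 describes the tilt test as 15 minutes flat followed by up to 45 minutes upright under continuous monitoring. Follow-up is one lying and one standing reading at 3 minutes. Subtracting the first from the second yields a change that contains the difference between the tests as well as any effect of treatment.

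An open choice of measure and of period-2 baseline also leaves room for selection after data are seen, and a listed outcome has no scheduled post-treatment observation.

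**Working it through.** **1. The plan's own sample size.** Inputs from Power Analysis: difference 10, SD 7.5, two-sided alpha 0.05, power 0.8, two groups. Normal approximation: n per group = 2 × (1.960 + 0.842)² × (7.5/10)² = 8.83, rounded up to 9, so 18 in total. Dividing by 0.9 for drop-out gives 20. The stated figures reproduce (with the t-test itself, power is 0.757 at 9 per group and 0.805 at 10). The calculation does not show which heart rate has the SD of 7.5.

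**2. Does the effect carry over between measures?** 10/100 = 10% of the level in the example; 10/30 = 33% of a rise at the diagnostic threshold. If 7.5 is the SD of a single reading and lying and standing correlate at c (assumed), the SD of the rise is 7.5 × √(2(1 − c)): 8.87 at c = 0.3 and 5.81 at c = 0.7. Neither the effect nor the SD transfers automatically.

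**3. What the visit text lets one compute.**

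| Visit | Tilt | Lying and standing |
|---|---|---|
| 2 (before treatment) | yes | yes |
| 4 (end of period 1) | no | yes |
| 5 (after washout) | no | yes |
| 7 (end of period 2) | no | yes |

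Expected completers: 20 × 0.9 = 18, of whom 0 have a scheduled post-treatment tilt test. At most the 2 expected drop-outs would have one attempted.

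**4. Effect of a tilt baseline.** Write T for the Visit 2 tilt value, B for the Visit 2 orthostatic value, and d = T − B for the offset.
- Within-treatment change: V4 − T = (V4 − B) − d. The offset remains.
- Period contrast with the same baseline for both periods: (V7 − T) − (V4 − T) = V7 − V4. The baseline drops out.

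**5. Effect of the period-2 baseline.** Assume equal correlation r between visits and s = 7.5 for a single reading.
- V7 − V4 has variance 2s²(1 − r).
- (V7 − V5) − (V4 − V2) has variance 4s²(1 − r), twice as large.

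For 18 completers and a paired t-test (half-width = 2.110 × SD/√18):

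| r | Contrast | SD | 95% half-width | Power for 10 beats/min |
|---|---|---|---|---|
| 0.3 | V7 − V4 | 8.87 | 4.41 | 0.994 |
| 0.3 | own baseline per period | 12.55 | 6.24 | 0.890 |
| 0.7 | V7 − V4 | 5.81 | 2.89 | >0.999 |
| 0.7 | own baseline per period | 8.22 | 4.09 | 0.998 |

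**6. Chance of a false positive if the choice were free.** Simulation under no drug effect: 18 patients, normal data, equal variance in both postures, two-sided paired t-test at 0.05, lying/standing correlation 0.3 to 0.8. Each figure is the chance that at least one of the listed tests is significant.

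| Measures open | V7 − V4 only | Period-2 baseline also open |
|---|---|---|
| one fixed measure | 5% | not run |
| lying, standing | 8-10% | 13-16% |
| lying, standing, rise | about 12% | about 20% |

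The paired t-test is an assumption: the plan says only t-tests for the analysis and names a two-sample test for the sample size.

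**The case against.** The strongest reply is that the plan is less open than it looks. The endpoint sentence gives one month, the visit list places that at Visits 4 and 7, and a source for baseline heart rate is named. The power example of 100 to 90 is plausible for a level and not for a lying-to-standing rise, and the hypothesis concerns tachycardia, which Section 5 defines as a rate above 100. On that reading only lying and standing compete, and the lower simulated figures apply. This stands as a narrowing: the rise is the less likely reading. It does not settle posture, because the example names none.

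A reader might infer several stronger things that the documents do not support:
- *That no time point or baseline is given.* Both are. What is missing is the reading within the visit, and a baseline that matches the follow-up test.
- *That the ivabradine-placebo comparison is biased by the tilt baseline.* A constant offset cancels there (step 4).
- *That the study loses its planned power.* Under the assumptions of step 5, within-patient power stays at about 89% or more.
- *That results will be watched and the measure then chosen.* Statistical Analysis says only that the design is adaptive and analysed in batches, with the investigator and analysts blinded. It describes no treatment comparison at a batch and no selection of a measure.
- *That 12% or 20% is an upper limit.* These figures count three measures only; the listed mean and maximum are not included.

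It is also fair to say that this is a 20-patient proof-of-concept study, and that Figure 1 was not available. If the figure shows a post-treatment tilt test, the tilt part weakens and the unnamed measure remains.

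**Conclusion.** The point holds in this form. The primary endpoint selects neither lying rate, standing rate nor rise, and the mean, maximum and average heart rates in the analysis text are tied to no test. The baseline rule as written pairs a tilt test with a different follow-up test. The resulting offset is harmless in the treatment contrast but remains in the within-ivabradine change, which is how Specific Aim 1 words the primary endpoint. The period-2 baseline is unstated. By the visit text, the before/after tilt outcome cannot be estimated in any of the 18 expected completers.

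The cost of leaving this open is a result whose meaning depends on an unrecorded choice, and a false-positive rate that could rise from 5% to roughly 8-12%, or 13-20% with the baseline also open. Those ranges rest on the assumptions in step 6 and illustrate free choice; they do not predict what the investigators will do. This is more than missing detail, because a stated rule gives a wrong change score and a stated outcome has no scheduled data. It should be corrected before any batch is analysed.

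**What to change.** Before any batch is analysed:

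1. Name one orthostatic measure as primary, with posture and minute of reading, compared within patient between Visits 4 and 7. Which measure is for the investigators to choose and justify. Make the other orthostatic measures secondary.
2. For any change score, use the Visit 2 orthostatic reading as baseline, not the tilt value.
3. State whether Visit 5 is the period-2 baseline or only a check for carry-over.
4. Confirm that the 10 beats/min effect and the SD of 7.5 apply to the named measure.
5. Reconcile the tilt statements in Specific Aim 1, Study Visits, Assessments and Drop-outs. The option without added procedures is to limit tilt to characterising patients at entry and drop it from the before/after outcomes; the price is giving up a tilt-based efficacy claim. The alternative is to schedule post-treatment tilt tests, which adds procedures.
6. Tie the maximum heart rate to a scheduled test or remove it.

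With the first option under item 5, the cost is one protocol amendment and a re-check of the sample-size inputs. No visit is added, because orthostatic heart rate is already taken at all seven.

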**Statistical Analysis.** Continuous variables including mean heart rate, maximum heart rate, and quality of life scores will be summarized using descriptive statistics, including the number of observation (n) mean, standard deviation (SD), standard error (SE), median, the 1st (Q1) and 3rd (Q3) quartiles, minimum, and maximum values. The change in heart rate at one month from baseline will be compared by T-tests based on treatment status with placebo versus Ivabradine. Categorical variables will be compared by McNemar's test based on treatment status with placebo versus Ivabradine.

The study design will be adaptive and data analysis will be done in batches. The PI and others involved in data analysis will be blinded to who is the Ivabradine group and who is in the placebo group.

**Power Analysis.** Assuming a decrease in average heart rate of 10 beats/min is clinically significant (e.g. Decrease from 100 to 90; magnitude of effect 10%) with power 0.8 and standard deviation in heart rate is 7.5 beats/min, the estimated sample size is 18 patients. We will enroll 10 patients in each group to account for the 10% drop-out rate and to ensure the study is adequately powered. For sample size calculation, two-sided alpha level = 0.05 and two sample t-test are used.

**Drop-outs.** If any patient decides to withdraw from the study due to the intolerance of side-effects, we will try to obtain a tilt table test, orthostatic heart rate, QOL questionnaire, and blood tests at the time of drop-out.

**Documentation.** All patient related documentation will be stored at UCSD for future analysis as funding becomes available. To minimize the potential loss of confidentiality, patients will be assigned a unique number as their subject identifier code. The unique subject code will be used to label all study documents. The key that relates the code numbers to the individuals will be kept in a locked cabinet in the PI's office at the ACTRI.

All procedures mentioned above are research procedures and are not part of standard care.

Results may be used for diagnosis, treatment, and prevention of disease in patients.

**Incidental findings that result from the conduct of this study that require medical intervention for the subject will be noted by the PI or her project's medical research staff. They will refer the subject to his primary care physician. If the subject does not have a primary care physician one will be appointed for him or her.**

---

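### The endpoint labelled primary compares the ivabradine month with baseline and names no placebo comparator, while the only heart-rate test and the sample size compare ivabradine with placebo

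*Combined protocol and SAP*

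**What the plan says.** Three places describe the heart-rate comparison.

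- **Section 6, Specific Aim 1**, the only place with a primary endpoint label: "Change in heart rate after one month of Ivabradine intervention compared to baseline". The secondary endpoint, quality of life, has the same form: ivabradine month against baseline, no placebo.
- **Section 9, Statistical Analysis**, the only place that names a test for heart rate: "The change in heart rate at one month from baseline will be compared by T-tests based on treatment status with placebo versus Ivabradine". It does not call this test primary.
- **Section 6, introductory text**: "We will compare heart rates in both groups after one-month of intervention". This sentence mentions neither baseline nor a test.

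The Power Analysis in Section 9 begins "Assuming a decrease in average heart rate of 10 beats/min is clinically significant" and illustrates this with a decrease from 100 to 90. It then states that "two-sided alpha level = 0.05 and two sample t-test are used". No sentence connects the labelled endpoint to the placebo comparison, or says which one the trial's conclusion rests on.

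**The concern.** A change from baseline on ivabradine mixes the drug effect with whatever else moves heart rate between baseline and the end of the month. In ivabradine minus placebo, a fall shared by both treatments cancels. In the endpoint as labelled, it counts in full.

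The protocol itself points to possible sources of such a shared fall. Patients taking midodrine, Florinef or ivabradine have a one-week washout around baseline testing (Section 9, Assessments), and Section 14 warns that washout may provoke tachycardia, so some baselines may be temporarily high. The Visit 2 baseline heart rate is taken from a tilt test, whereas Visits 4 and 7 list only orthostatic monitoring. If the tilt value serves as baseline, any systematic difference between the two procedures enters the before/after contrast.

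A trial built around a placebo month could therefore report, as its labelled primary result, a quantity that the placebo month does not inform. While the plan leaves the two contrasts unreconciled, the choice between them could also be made after the results are known.

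**Working it through.** **1. Which contrast does the sample size support?** Inputs, all from the Power Analysis: difference 10, SD 7.5, "with power 0.8", two-sided 0.05, two-sample t-test.

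n per arm = 2 × (1.960 + 0.842)² × 7.5² / 10² = 2 × 7.849 × 0.5625 = 8.83, rounded up to 9. The total is 18, which matches "standard deviation in heart rate is 7.5 beats/min, the estimated sample size is 18 patients". Dropout: 18 / 0.9 = 20, which matches "We will enroll 10 patients in each group to account for the 10% drop-out rate". (The exact noncentral t gives 75.7% power at 9 per arm and 80.5% at 10, so the normal approximation was evidently used.)

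A one-sample before/after test, if 7.5 is taken as the SD of the change, would need (1.960 + 0.842)² × 7.5² / 10² = 4.41, that is 5 patients. The stated 18 is therefore the two-arm, placebo-controlled calculation. It does not size the labelled endpoint.

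**2. How far apart can the two contrasts be?** From the plan: 18 completers, SD 7.5 per reading, two-sided 0.05. Assumed, because the documents give no values: within-patient correlation ρ of 0.3 to 0.7, and a fall common to both treatments of 2 to 5 beats/min. Drug effect zero, no carryover or period effect, one common baseline.

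- SD of (ivabradine − baseline) = 7.5 × √(2(1 − ρ))
- Standard error = that SD / √18
- Noncentrality = common fall / standard error
- Chance of a significant result in favour of ivabradine = upper tail of the noncentral t (17 df) beyond 2.110

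| ρ | SD of change | SE | fall 0 | fall 2 | fall 3 | fall 5 |
|---|---|---|---|---|---|---|
| 0.3 | 8.87 | 2.09 | 2.5% | 15% | 27% | 62% |
| 0.5 | 7.50 | 1.77 | 2.5% | 19% | 36% | 76% |
| 0.7 | 5.81 | 1.37 | 2.5% | 28% | 54% | 93% |

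Example: ρ = 0.5 and a fall of 3 give noncentrality 3 / 1.77 = 1.70 and probability 36%. Simulation with 40,000 trials per setting agrees to within about one percentage point.

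For ivabradine minus placebo within patient, the common fall drops out and the rate stays near 2.5% in every setting. At a common fall of 3, the before/after test is positive and the placebo contrast is not in about 25% to 52% of simulated trials.

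**3. Do the two placebo comparisons differ from each other?** With one common baseline and a within-patient analysis, (ivabradine − baseline) − (placebo − baseline) = ivabradine − placebo. The sentence in the introduction to Section 6 and the test in Section 9 are then the same comparison.

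**4. Is the placebo contrast affordable?** With 18 completers and a 10 beats/min effect, a paired test of ivabradine minus placebo has 96.4% power at ρ = 0, 99.4% at ρ = 0.3 and over 99.9% at ρ = 0.5 or more.

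**The case against.** The best defence is that Specific Aim 1 names the patient-level variable, change from baseline, just after describing a placebo-controlled crossover, and that Section 9 takes the same variable and supplies the comparison. No test of ivabradine against baseline appears anywhere, and the sample size is two-arm. This is probably the intent, and it stands as evidence of intent. But the protocol never says so, and the secondary endpoint repeats the same uncontrolled form. On this reading the labelled endpoint still has to be reworded to match the test and the sample size.

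Some stronger readings are not supported:

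- *Three rival deciding comparisons.* Only one is labelled primary, only one has a test, and the third is a design sentence. The two placebo comparisons coincide under step 3. They separate only under an unpaired or first-period analysis, or with a separate baseline for each period.
- *The plan as written will declare success without a drug effect.* That needs a before/after test, which the plan does not specify. The risk arises if the labelled endpoint is the one reported.
- *No earlier work had a placebo group.* The remark in Section 7 refers to case reports.
- *Stable salt and fluid intake would lower heart rate.* Section 9 describes it as part of the washout protocol, with intake held steady.

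It is also fair that the table illustrates a general weakness of uncontrolled comparisons under assumed inputs. It does not measure an error in the Section 9 test.

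**Conclusion.** The point holds as a conflict between two contrasts. The labelled primary endpoint cannot answer the trial's placebo-controlled question, the named test and the sample size can, and the protocol does not reconcile them.

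If the endpoint is reported as labelled and there is no drug effect, the rate of significant results in favour of ivabradine rises from 2.5% to about 27% to 54% for a common fall of 3 beats/min. These figures rest on an assumed fall and an assumed correlation, neither of which the documents give. If there is no common fall, there is no inflation. The conflict in wording is there whatever the size of the fall, and it should be settled before any treatment comparison is seen.

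**What to change.** - **Section 6, Specific Aim 1:** define the primary endpoint as the difference between ivabradine and placebo in change in heart rate from baseline at the end of the one-month treatment period (Visits 4 and 7). Change from baseline need not be dropped. With a common baseline and a within-patient analysis, this equals the end-of-period ivabradine minus placebo difference. Say which visit supplies the baseline, since that equality depends on it.
- **Section 9, Statistical Analysis:** state that this contrast is the primary test, at two-sided 0.05.
- **Section 6, introductory text:** align the sentence on comparing heart rates with this definition.
- Report the ivabradine change from baseline only as a descriptive summary.

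The cost is wording in three places, with no new visits, data or patients. The downside is that the before/after fall can no longer be presented as the primary result.
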